11.17 Criterion Flags

- Subjects who are alive at the given timepoints with the below mentioned criteria will be flagged as 'Y' in the analysis datasets. All subjects within Per-Protocol and FAS will be flagged irrespective of their disposition status. Any ambiguity in subject status will be considered as failure and flagged as 'N'.

Criterion Flag	Criteria	Other Criteria
Flag 01	Alive on Day 14	Without the following (end date prior to day 14): 
 • Ongoing use of vasopressors • Ongoing intubation/mechanical ventilation

		
 • New ongoing need for dialysis/renal replacement therapy (RRT)
Flag 02	Alive on Day 7	Without the following (end date prior to day X):
Flag 03	Alive on Day 14	
 • Ongoing use of vasopressors
Flag 04	Alive on Day 28	
 • Ongoing intubation/mechanical ventilation
Flag 05	Alive on Day 60	
 • Ongoing residence in an ICU
Flag 06	Alive on Day 90	
 • New ongoing need for dialysis/renal replacement therapy (RRT)

- Subjects who were discharged will be flagged 'Y' in the analysis datasets based on the following criteria:

Criterion Flag	Criteria
Flag 07	Discharged on Day 14
Flag 08	Discharged on Day 28
Flag 09	Discharged on Day 60
Flag 10	Discharged on Day 90

If a subject does not meet the given criteria, they will be flagged as 'N'. All subjects within Per-Protocol and FAS will be flagged irrespective of their disposition status.

11.18 Time to Death

Time to Death will be calculated as follows:

- Time to Death = (Date of Death – Date of First IMP) + 1

Subjects without death in the trial will be censored at either the date of withdrawal or the date of last visit, whichever occurs earlier.

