## **6.5. Study Duration**

Subjects will be treated with 3 doses over 36 hours: after the initial dose is administered (Dose #1), then next dose (Dose #2) is administered 12 hours later, and the last dose is administered 24 hours later (Dose #3 administered 36 hours after Dose #1).

Subject screening will occur for Part 1 within 24 hours of determination of WHO severity score of 4 to 6, whether the severity score is attained on admission or during current ongoing hospitalization, or for Part 2, within 24 hours of intubation without ECMO with a WHO severity score of 6 or 7. Eligible subjects will be randomized within 12 hours of informed consent (Part 1) or 24 hours of intubation (Part 2), and dosed within 12 hours of randomization (both parts).

Subjects are followed for safety and efficacy through Day 90.

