## **6.8. Criteria for Treatment Discontinuation**

Subjects are free to discontinue their participation in the study at any time and without prejudice to further treatment. The Investigator must withdraw any subject from the study if that subject requests to be withdrawn, or if it is determined that continuing in the study would result in a significant safety risk to the subject.

The subject's participation in this study may be discontinued for the following reasons:

- Subject withdrew consent
- Unacceptable AE
- Subject is unwilling or unable to continue the study or is lost to follow up
- Subject is non-compliant with study procedures/study protocol
- Investigator decides that withdrawal from the study is in the best interest of the subject
- Any clinically significant change in subject's medical condition (at the discretion of the Investigator)
- Sponsor decision to end the study

If a subject withdraws from the study prematurely, assessments scheduled for the EOS Visit should be performed ASAP. If a subject refuses further assessment, the subject should be contacted for safety evaluations (AE/concomitant medications/potential pregnancy) approximately 28 and 90 days after study withdrawal.

If such withdrawal occurs, or if the subject refuses to participate in the EOS Visit, the Investigator must determine the primary reason for a subject's withdrawal from the study and record the information on the electronic case report form (eCRF). If the reason for withdrawal is an AE, monitoring should continue until the outcome is evident. The specific event or test result(s) must be recorded in the eCRF. At the discretion of the Sponsor, subjects may also be removed from the study.

It should be clearly documented in the source data whether a subject withdrew his/her consent and will not enter the follow-up phase, or if a subject withdrew his/her consent for study drug treatment but will continue further participation in the study.

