#### **10.1.2. Serious Adverse Event (SAE)**

An SAE is an AE occurring during any study phase (i.e., baseline, treatment, or follow up), and at any dose of the investigational product, comparator or placebo, that fulfills one or more of the following:

- Results in death
- It is immediately life-threatening
- It requires in-patient hospitalization or prolongation of existing hospitalization
- It results in persistent or significant disability or incapacity
- Results in a congenital abnormality or birth defect
- It is an important medical event that may jeopardize the subject or may require medical intervention to prevent one of the outcomes listed above.

All SAEs that occur after the subject/next of kin/legal proxy has given informed consent and has been randomized, including before or during treatment and within 90 days following the last dose of study drug, whether or not judged to be related to the study, must be recorded on forms provided by the Sponsor.

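### Time to death is censored at the earlier of withdrawal and last visit, which discards known-alive follow-up, and the SAP does not say whether a death after withdrawal is an event

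*SAP*

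**What the plan says.** SAP 11.18 defines the event time as "Time to Death = (Date of Death – Date of First IMP) + 1". The censoring rule follows: "Subjects without death in the trial will be censored at either the date of withdrawal or the date of last visit, whichever occurs earlier". The SAP does not define what makes a death one *in the trial*, or whether withdrawal means withdrawal from study drug or from the study.

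This variable feeds the Kaplan-Meier survival estimates at Days 28 and 90 and the log-rank test (SAP 12.9.2.2.1), the Cox model (12.9.2.2.2) and the survival curves (12.9.2.2.3). All-cause mortality at Days 28 and 90 and time to death are secondary endpoints (Protocol 5.2.2).

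The protocol provides several sources of information after withdrawal:

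- Planned follow-up (6.5): "Subjects are followed for safety and efficacy through Day 90".
- At premature withdrawal (6.8): "assessments scheduled for the EOS Visit should be performed ASAP".
- For those who refuse further assessment (6.8): "the subject should be contacted for safety evaluations (AE/concomitant medications/potential pregnancy) approximately 28 and 90 days after study withdrawal".
- Withdrawal from treatment only is foreseen, since 6.8 has sites document "if a subject withdrew his/her consent for study drug treatment but will continue further participation in the study".
- SAEs, which include fatal events, that occur "within 90 days following the last dose of study drug, whether or not judged to be related to the study, must be recorded" (10.1.2).

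**The concern.** All-cause mortality is normally censored at the date last known alive. Taking the earlier of two dates always selects the less informative one. If the last visit comes before withdrawal, the days between are lost. If it comes after, as with an end-of-study assessment following withdrawal or with visits after a drug-only withdrawal, everything past the withdrawal date is lost.

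The second problem is the event definition. SAP 11.5 lists death as one disposition reason beside consent withdrawal, adverse event and others. A subject who withdraws for another reason and later dies has a non-death disposition, and two programmers could reasonably code that subject differently.

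This matters because withdrawal here may be informative. The reasons listed in Protocol 6.8 include an unacceptable adverse event and a clinically significant change in medical condition. Kaplan-Meier, log-rank and Cox analyses all assume that a censored subject has the same later risk as those still followed. The SAP plans no sensitivity analysis of the censoring rule.

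**Working it through.** **The plan's own figures.** None is given for time to death: no event count, mortality rate, hazard ratio or withdrawal rate. The only power figure concerns the primary endpoint (Protocol 11.2: N=54, 20% vs 5%, one-sided alpha 0.2, about 80%). With 27 per arm, z = (0.15·√27 − 0.8416·√(2·0.125·0.875)) / √(0.16 + 0.0475) = (0.7794 − 0.3936)/0.4555 = 0.847, which gives power 0.801. The stated figure reproduces and does not depend on the censoring rule.

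**When the contacts fall.** A subject who withdraws on Day 10 would be contacted at about Day 10 + 28 = Day 38 and Day 10 + 90 = Day 100. Completed contacts would therefore settle status at both landmarks, Day 28 and Day 90.

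**Illustration, one arm of 30 (Protocol 7.1).** The rest is assumed:

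- D other deaths, on the first D of Days 5, 9, 14, 20, 27 and 40.
- w withdrawals on Day 10, with w from 1 to 3 (3.3% to 10% of the arm).
- x of the withdrawn subjects die on Day 24 and this becomes known.
- Everyone else is alive at Day 90.

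The estimate is S(t) = ∏(1 − dᵢ/nᵢ). With status known for all, mortality is the number of deaths by that day divided by 30.

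Worked case, D=4, w=2, x=2, Day 28. Two deaths occur before Day 10, so S = 28/30. Censoring both withdrawals leaves 26 at risk, and two more deaths leave 24. S = 28/30 × 24/26 = 0.862, so mortality is 13.8%. With both later deaths counted it is 6/30 = 20.0%.

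| D | w | x | Day | Censored at withdrawal, later deaths not counted | Status known for all | Difference (points) |
|---|---|---|---|---|---|---|
| 4 | 1 | 1 | 28 | 13.6% | 16.7% | 3.1 |
| 4 | 2 | 2 | 28 | 13.8% | 20.0% | 6.2 (3.1 per death) |
| 6 | 3 | 3 | 90 | 21.6% | 30.0% | 8.4 (2.8 per death) |
| 6 | 3 | 1 | 90 | 21.6% | 23.3% | 1.7 |
| 6 | 3 | 0 | 90 | 21.6% | 20.0% | −1.6 |
| any | 0 | 0 | either | same | same | 0 |

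**Bound.** Early censoring cannot bring the Kaplan-Meier mortality below D/30, and full follow-up gives (D + x)/30. The shortfall is therefore at most x/30, or 3.3 points per uncounted death. For one withdrawal before all D other deaths it is (D+1)/30 − D/29 = 1/30 − D/870, which falls as D rises.

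**The opposite reading.** Take D=6, w=3, x=1 at Day 90. Count the later death, but censor the two withdrawn survivors at Day 10. Then 26 are at risk after Day 10 and five deaths leave 21. S = 28/30 × 21/26 = 0.754, so mortality is 24.6%, against 7/30 = 23.3% with full status. The same data thus give 21.6% or 24.6% depending on how one undefined phrase is read, and neither equals 23.3%.

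**The case against.** A reader might infer that the SAP drops deaths after withdrawal. The text does not say so. The event formula has no cut-off at withdrawal, and the censoring sentence covers only subjects without an in-trial death. Loss of later deaths follows only if that phrase means before withdrawal. What the documents support is an undefined term. That objection stands.

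A reader might also infer that the protocol secures vital status after withdrawal. It does not. The 28- and 90-day contact applies only to subjects who refuse further assessment, is worded as a recommendation, and names adverse events, medications and pregnancy rather than survival. Protocol 6.8 also foresees subjects who withdraw consent and do not enter follow-up, and 10.7 lists consent withdrawal among the points at which AE and SAE follow-up ends. Information after withdrawal is possible but not assured. Still, a completed safety contact does show whether the subject was alive.

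The daily phone calls to discharged subjects through Day 14 (Protocol 6.6) add little. Discharge is not withdrawal, and later visits normally set the last-visit date.

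On consequences, the objection is largely right. SAP 12.9.1.1 and 12.9.2.3 count discontinued subjects as failures in the binary endpoints, so the primary result does not use this rule. SAP 12.10.2 tabulates all-cause deaths on the Safety set without it. Protocol 11.1 calls log-rank and Cox analyses supplemental, and SAP 8.2 urges caution with secondary tests. These points limit the importance of the defect but do not remove it. The earlier-date rule is explicit, and the death table and the Kaplan-Meier event count could disagree.

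**Conclusion.** The point holds as a defect in a secondary derivation. The rule discards known-alive time wherever the protocol has collected it after the earlier date, and it leaves the event status of a death after withdrawal undefined. Either reading is worse than censoring at the date last known alive: one biases mortality downward when withdrawal is informative, the other biases it upward.

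The size rests on assumed cases, because the documents give no withdrawal or death rates. In an arm of 30, each uncounted death costs about 3 points of Kaplan-Meier mortality, and less on balance when other withdrawn subjects survive. The value 1/30 = 3.3 points might be taken as a minimum per missed death, but it is the maximum. If no withdrawn subject dies, the change in these cases is at most 1.6 points; without withdrawals it is zero. The treatment comparison is disturbed mainly if the arms differ in withdrawals or in later deaths among those withdrawn. The primary endpoint is unaffected.

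**What to change.** Reword SAP 11.18 before unblinding:

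- Count every death reported through the Day 90 window as an event, whether or not the subject had withdrawn from drug or study.
- Censor all other subjects at the date last known alive, using any data collected under the protocol and permitted by the subject's consent (visit, phone call, post-withdrawal safety contact, SAE follow-up), capped at the Day 90 window.
- Add a sentence explaining why discontinued subjects are failures in the binary endpoints but censored here, and report by arm how many have unknown status at Days 28 and 90.

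The cost is one revised derivation and a short paragraph, with no new data collection. Status will remain incomplete for subjects who refuse contact, so the change reduces the problem without removing it.

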11.19 Self-Evident Corrections

In some instances, spelling errors may be corrected in analysis mapping for 'Other, Specify' fields (free text). These will be reconciled and confirmed during clean file meeting.

12 Statistical Analysis

12.1 Subject Disposition

Number of subjects in screened, all-enrolled and randomized Analysis Set, number and percentage for subjects in safety Analysis Set, FAS, per protocol Analysis Set, subjects who completed the study, study duration (days), number of subjects who terminated the study early along with their reasons will be summarized by treatment. Reason for discontinuation will be displayed in the descending order of "Total" column.

Screened and All-enrolled Analysis Set will be presented only for Total columns. All other summaries will be presented by treatment groups. A CONSORT flowchart will also be presented to visualize the flow of disposition.

Note that randomized Analysis Set will be displayed by planned treatment and all other categories will be displayed by actual treatment.

Percentages will not be displayed for screened and all-enrolled Analysis Set. The percentages by treatment group for randomized analysis set will be based on all-enrolled Analysis Set. All other percentages will be based on randomized Analysis Set. Percentages for categories of reason for discontinuation from the study will be based on the number of subjects who discontinued from the study.

In DDP: Table 14.1.1.1, Figure 14.1.1.1

Subject disposition information, status of inclusion exclusion criteria, randomization details and subjects excluded from Analysis Set along with reasons will be listed by subject. All derived variable summarized in the tables will also be listed.

In DDP: Listings 16.2.1.1, 16.2.1.2, 16.2.1.3 and 16.2.3.1

12.2 Visit Attendance

Number and percentage of subjects who attended each visit (Screening, Day 1, Day 2, Day 3, Day 7, Day 14, Day 28, Day 60, Early Withdrawal and End of Study) will be summarized by treatment group. Percentages will be based on FAS.

In DDP: Table 14.1.2.1

12.3 Protocol Deviations

Number and percentage of subjects with any deviation and number of deviations will be summarized by treatment. The same will be sub-classified by grade (important/not important) and category (Informed consent deviation, Entry Deviation, Dosing Deviation, Withdrawal Deviation, Operational Deviation, Other, COVID-19 Deviation etc.). Deviation categories will be displayed in descending order of the “Total” column.

Percentages will be based on Randomized Analysis Set.

In DDP: Table 14.1.3.1

Protocol deviations will be listed by subject.

In DDP: Listing 16.2.2.1

12.4 Demographic and Baseline Characteristics

Subject demographics will be summarized by treatment. Categorical and continuous variables will be provided in the same table. The following variables will be presented: age (years), sex, ethnicity, race, height (cm), weight (kg), BMI (kg/m²), childbearing potential and methods of birth control for the subject as well as the partner. Percentages will be based on the non-missing results within the Analysis Sets. Percentages for Childbearing potential and method of birth control will be based only on female population. Method of birth control for the subject’s partner will be based only on the male population reporting birth control.

The summaries will be repeated for all randomized, FAS, per protocol and PK Analysis Sets (as per ICH E3 Guidelines). Note that Safety Analysis Set and FAS are same as per definition; hence, the analysis is not repeated for the Safety Analysis Set.

In DDP: Table 14.1.4.1, 14.1.4.2, 14.1.4.3 and 14.1.4.4

Subject demographics will be listed by subject.

In DDP: Listing 16.2.4.1

12.5 Baseline Characteristics

Descriptive statistics for the baseline diagnostic parameters will be summarized by treatment group. The parameters will include: Temperature (°C), Heart Rate (beats/min), Respiratory Rate (breaths/min), Oxygen Saturation (%), Ferritin, D-Dimer, CRP, and Procalcitonin.

The summaries will be repeated for FAS and per-protocol Analysis Sets. If all the Analysis Sets are same, summary will be presented only for FAS. Note that Safety Analysis Set and FAS are same as per definition; hence, the analysis is not repeated for the safety analysis set.

In DDP: Table 14.1.5.1 and Table 14.1.5.2

Baseline Diagnostic Criteria will be listed by subject.

In DDP: Listing 16.2.4.2

12.6 Medical/Surgical History

Number and percentage of subjects with any medical / surgical history and number of events will be summarized by treatment. The same will be classified by System Organ Class (SOC) and Preferred Term (PT). The SOC and PT will be displayed in the descending order of frequency in “Total”. Medical history will be coded using the Medical Dictionary for Regulatory Activities (MedDRA) version 23.0 or Higher.

Percentages will be based on Safety Analysis Set.

The summary will be presented for medical / surgical history and concurrent diseases separately. History and Concurrent Diseases will be flagged as mentioned in Section 11.10.

In DDP: Tables 14.1.6.1 and 14.1.6.2

Medical/Surgical History will be listed by subject and body system.

In DDP: Listing 16.2.4.3

12.7 Prior and Concomitant Medications

Number and percentage of subjects who have taken any prior / concomitant medication will be summarized by treatment and study period. The same will be classified by Therapeutic Main group (ATC Level 2) and Chemical Subgroup (ATC Level 4). If ATC level 4 is missing, ATC levels 2 or 3 will be used. The therapeutic main group and chemical subgroup will be displayed in the descending order of

frequency in "Total" for Treatment Period. Medications will be coded using the World Health Organization's Drug-Dictionary (WHODrug) version September 2020 or latest.

Percentages will be based on Safety Analysis Set.

The summary will be presented for prior and concomitant medications separately. Prior and concomitant medications will be flagged as mentioned in section 11.11.

In DDP: Tables 14.1.7.1 and 14.1.7.2

All medications will be listed by subject and therapeutic subgroup. Prior and concomitant medications will be flagged. Subjects will be grouped by treatment.

In DDP: Listing 16.2.4.4

12.8 Extent of Exposure

Number and percentage of subjects exposed to treatment over time (1st dose, 2nd dose, and 3rd dose), cumulative planned IV to be administered (mL), cumulative actual IV administered (mL), % compliance, and number and percentage of subjects with dose interruptions for each dose (1st dose, 2nd dose, and 3rd dose) along with reason for interruptions will be summarized by treatment. Both continuous and categorical summary will be presented in the same table. Percentages will be based on FAS. Percentages for reason for interruptions will be based on the number of subjects whose dose was interrupted in the respective dose.

In DDP: Table 14.1.8.1

IV administration data will be listed by subject for FAS. Subjects will be grouped by treatment.

In DDP: Listing 16.2.5.1

12.9 Efficacy Analyses

All efficacy analyses will be based on FAS. Analyses will be repeated for Per-Protocol Analysis Set to check the robustness of the results (sensitivity analyses).

12.9.1 Primary Efficacy analysis

12.9.1.1 Proportion of Subjects Alive on Day 14

Number and percentage of subjects alive on Day 14 without the following will be summarized. Percentages will be based on the corresponding analysis set. Subjects who discontinued from the study early or whose survival status is inconclusive on Day 14 will be considered as failure (Not Alive).

- Ongoing use of vasopressors
- Ongoing intubation/mechanical ventilation
- New ongoing need for dialysis/renal replacement therapy (RRT)

The proportion of subjects alive will be compared across treatment arms using a Cochran-Mantel-Haenszel (CMH) method. The common Risk Difference along with associated 80% CI will be reported. Unadjusted p-value for testing the null hypothesis that there is no strong correlation between treatment and subject status will also be reported. As this is a pilot Phase 2 proof-of-concept (POC) trial in an infection with no approved therapy and false negative error (100% minus power) is equally as important as false positive error, the one-sided type 1 error is set at 0.2.

Reference SAS Program:

```
proc freq data= ;
  tables <status>*<treatment> / cmh riskdiff(common) alpha=0.2;
run;
```

The analyses will be based on FAS and repeated for Per-Protocol Analysis Set.

In DDP: Tables 14.2.1.1 and 14.2.1.2, Listing 16.2.6.2, 16.2.6.3, and 16.2.6.4

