## 11. STATISTICS

### 11.1. General Overview

All subjects given e 1 dose of study drug will be included in the Full Analysis Set (FAS) according to actual drug received; non-completers will be counted as failures in the primary efficacy analysis. Subjects receiving all 3 doses and evaluable for the primary Day 14 endpoint will constitute the per-protocol population for efficacy assessment. WHO severity score will be recorded daily while the subject is hospitalized, after discharge through Day 14, where feasible, and at each follow-up visit.

AE data will be summarized for the FAS by actual drug received using counts and proportions of subjects having an AE, each AE type, and an AE of each System Organ Class. SAEs and reasons for any early discontinuation will be summarized similarly. All deaths will be categorized by cause of death as per investigator assessment and relationship to study drug and/or COVID-19

Immunogenicity will be assessed on Days 1(predose), 28, and 90 days in all participants. Antibodies against pGSN will be assayed from frozen specimens to determine whether the investigational product induces an antibody response in recipients.

For Part 1, binary efficacy endpoints will be compared between treatments via stratified Cochran-Mantel-Haenszel (CMH) test and, to accommodate continuous covariates, via logistic regression. Continuous efficacy and biochemical endpoints will be compared between treatments via mixed model repeated measures analysis or analysis of covariance, depending on whether repeated measures are available or not. Time-to-event analysis via stratified log rank test and Cox proportional hazards model may also be carried out as supplemental analyses.

For Part 1, exploratory analyses looking at biomarkers and outcomes in each treatment arm will be conducted. Other exploratory analysis to compare the efficacy endpoint data from the rhu-pGSN group from this study to that of external control data may be carried out if appropriate. Sample size may be increased to improve the precision of the estimates of between-treatment comparisons if appropriate and if drug supplies are available.

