11.5 Discontinued Subjects

Discontinued subjects will have safety assessments taken at Early Withdrawal visits. These will be presented separately and will not be combined with EOS if results are available.

The reason for discontinuation from the study will be mapped in the analysis as follows:

Primary reason for early discontinuation (As in CRF)	Reason for early termination from the study
Subject withdrew consent	Subject withdrew consent
Unacceptable AE	Unacceptable AE
Pregnancy	Pregnancy
Subject is unwilling or unable to continue the study or is lost to follow up	Subject unwilling / lost to follow-up
Subject is non-compliant with study procedures/study protocol	Protocol Deviation
Investigator decides that withdrawal from the study is in the best interest of the subject	At the discretion of the Investigator
Any clinically significant change in subject's medical condition (at the discretion of the Investigator)	At the discretion of the Investigator due to change in medical condition
Treatment unblinded	Treatment Unblinded
Sponsor decision to end the study	Sponsor decision to end the study
Death	Death
Other	Other

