11.16 Efficacy Endpoints

11.16.1 Hospitalization due to COVID-19

- Days in X = (End Date of X - Start Date of X) + 1
- Cumulative X Days = Sum of all (Days in X)

Note: X denotes Hospitalization, Intensive Care Unit (ICU) and Intubation / Mechanical Ventilations.

- Duration of COVID-19 illness before hospitalization (days) = (Initial Hospitalization Date – COVID-19 confirmation date) + 1

Note: The earliest COVID-19 confirmation date will be considered irrespective of whether or not it is prior to informed consent date.

If a subject has discontinued from the study and X is ongoing or the end date is missing, then X will be considered as ongoing at Day 14 for that subject. For cumulative X days calculation, disposition date will be considered as end date. If a subject had Ongoing Hospitalization at end of study, then end date is considered as subject's disposition date.

Note: X denotes Hospitalization, Intensive Care Unit (ICU) and Intubation / Mechanical Ventilations.

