12.9.2.2.4 Listing

Death Details will be listed by subject.

In DDP: Listing 16.2.7.4

12.9.2.3 Proportion of Subjects Alive on Days 7, 14, 28, 60 and 90

Number and percentage of subjects alive on Days 7, 14, 28, 60 and 90 without the following will be summarized. Percentages will be based on FAS. Subjects who discontinued from the study early or whose survival status is inconclusive on respective day will be considered as failure (Not Alive).

- Ongoing use of vasopressors
- Ongoing intubation/mechanical ventilation
- Ongoing residence in an ICU
- New ongoing need for dialysis/renal replacement therapy (RRT)

The analyses described in Section 12.9.1.1 will be repeated for each day as part of secondary analyses.

In DDP: Tables 14.2.4.1 and 14.2.4.2, Listing 16.2.6.2, 16.2.6.3, 16.2.6.4

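### The rule that scores early discontinuation as a Day 14 failure has no time limit, so a subject known to be a success on Day 14 can become a failure by leaving or dying later

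*SAP*

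**What the plan says.** Four places bear on how a subject who leaves is scored.

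- **SAP 12.9.1.1 (primary analysis):** "Subjects who discontinued from the study early or whose survival status is inconclusive on Day 14 will be considered as failure (Not Alive". There are two conditions joined by *or*. Only the second is visibly tied to a day.
- **SAP 12.9.2.3 (Days 7, 14, 28, 60 and 90):** the same construction, "Subjects who discontinued from the study early or whose survival status is inconclusive on respective day will be considered as failure (Not Alive".
- **SAP 11.17 (Flag 01 for the primary endpoint, Flags 02 to 06 for the secondary one):** the flag is built from survival and support on the named day. It adds "All subjects within Per-Protocol and FAS will be flagged irrespective of their disposition status" and "Any ambiguity in subject status will be considered as failure".
- **Protocol 11.1:** "non-completers will be counted as failures in the primary efficacy analysis". It does not say what has to be completed: dosing, Day 14 or Day 90.

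The meaning of *early* has to be taken from the disposition sections. Protocol 6.5 states "Subjects are followed for safety and efficacy through Day 90", and Protocol 6.7 puts the End of Study visit at Day 90. SAP 11.3 sets Early Termination beside End of Study as the two outcomes of that visit. The table in SAP 11.5, with its column "Primary reason for early discontinuation (As in CRF"), includes death. Protocol 6.9 foresees exits after the Day 14 visit.

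**The concern.** The SAP's own disposition terms tie *early* to leaving before Day 90. A programmer who uses the disposition variable to apply SAP 12.9.1.1 would therefore count withdrawals and deaths on Days 15 to 90 as Day 14 failures. A programmer who uses Flag 01 would not. The same subject can then have two different primary outcomes, each defensible from the SAP.

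Under the literal rule, events after the endpoint date change an outcome already observed. Equal re-scoring in both arms dilutes a real effect. Unequal re-scoring biases the comparison in either direction. The Per-Protocol repeat does not protect against this. SAP 10.6 requires Day 14 to be completed, all three doses taken and no important deviation affecting the primary endpoint, so a subject who leaves after Day 14 is not removed for leaving.

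**Working it through.** **1. The same subject under each rule.** Take a subject seen on Day 14 alive and off vasopressors, ventilator and dialysis, who withdraws or dies on Day 50.

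| Rule | Day 14 result |
|---|---|
| SAP 11.17, Flag 01 | Success: status on the day is known |
| SAP 12.9.1.1, literal | Failure: left the study before Day 90 |
| SAP 12.9.1.1, if the day limits both conditions | Success |
| Protocol 11.1 | Depends on what a non-completer is |

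Under the literal wording of SAP 12.9.2.3, this subject also fails Days 7 and 28, whatever was observed then. SAP 11.16.1 leans towards Flag 01. Its rule for Day 14 status reads: "If a subject has discontinued from the study and X is ongoing or the end date is missing, then X will be considered as ongoing". For discontinued subjects, that imputes ongoing hospital, ICU or ventilator time only where it is ongoing or undated.

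**2. The plan's own figures.** Inputs from Protocol 11.2 and SAP 4.2: N=54 (27 per arm), 20% and 5%, one-sided alpha 0.20 (z = 0.8416). I take 20% and 5% as failure rates, the only direction in which the drug helps.

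- Mean rate 0.125. Standard error under the null: √(2 × 0.125 × 0.875 / 27) = 0.0900.
- Standard error under the alternative: √((0.20 × 0.80 + 0.05 × 0.95) / 27) = 0.0877.
- Power: Φ((0.15 − 0.8416 × 0.0900) / 0.0877) = 0.801. The stated ~80% reproduces.
- The pooled test gives a minimum significant difference from 20% of 8.4 points at 27 per arm, as stated. At the 30 per arm of Protocol 7.1 it is about 8.0 points.

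**3. Effect of re-scoring.** Let *d* be the share of Day 14 successes who leave or die on Days 15 to 90. The documents give no value for *d*, so it is an assumed range. With the same *d* in both arms:

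- placebo failure rate = 0.20 + 0.80*d*
- rhu-pGSN failure rate = 0.05 + 0.95*d*
- difference = 0.15 × (1 − *d*)

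Exact power is the sum of the binomial probabilities of all count pairs with 30 per arm for which the one-sided CMH statistic exceeds 0.8416.

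| *d* | Placebo failures | rhu-pGSN failures | Difference (points) | Exact power |
|---|---|---|---|---|
| 0 | 20.0% | 5.0% | 15.0 | 0.86 |
| 2% | 21.6% | 6.9% | 14.7 | 0.81 |
| 5% | 24.0% | 9.75% | 14.25 | 0.76 |
| 10% | 28.0% | 14.5% | 13.5 | 0.69 |
| 20% | 36.0% | 24.0% | 12.0 | 0.57 |

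The normal approximation at 30 per arm shows the same pattern: 0.83, 0.74, 0.67 and 0.57 at 0, 5%, 10% and 20%.

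**4. Re-scoring in one arm only (30 per arm, exact).**

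- Only rhu-pGSN successes, *d* = 10%: 20% against 14.5% failures, power 0.40.
- No true difference (20% failures in both arms), only placebo successes re-scored: the one-sided rejection rate rises from 21.2% to 33.8% at *d* = 5% and 47.5% at *d* = 10%.

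**5. One subject can decide the test.** With 30 per arm, 6 against 3 failures gives one-sided CMH p = 0.141, significant at 0.20. Re-scoring one rhu-pGSN success gives 6 against 4, p = 0.246, not significant.

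**The case against.** The best reply is that the literal reading is not what the authors meant. The sentence stands under a heading about Day 14 and ends with that day, and its twin ends with the respective day. If the day governs both conditions, the rule means discontinued before, or unknown on, that day. The literal alternative makes a Day 60 withdrawal a Day 7 failure, which is absurd. The flag sentence in SAP 11.17 may mean only that every subject receives a Y or N and stays in the denominator. These readings are plausible and would reconcile the sections. But neither is stated, and the disposition terms point the other way. What stands of the objection is that this is an ambiguity with a probable benign intent, not proof that the sponsor meant to re-score late leavers.

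Three stronger inferences are tempting, and the documents do not support them.

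- *That failing a subject who leaves on Day 12 is an error.* Protocol 11.1 counts non-completers as failures. For subjects who refuse further assessment, Protocol 6.8 plans only safety contacts about 28 and 90 days after withdrawal. Day 14 support status may then be unknown, and SAP 11.17 would also give N.
- *That the label in brackets after failure contradicts the censoring in SAP 11.18.* It names one category of a binary table. Censoring is a convention for another endpoint, and deaths are reported separately in SAP 12.9.2.2 and 12.10.2.
- *That a large loss of power is to be expected.* No exit rate is given. At 2% in both arms exact power is 0.81, still about the planned 80%.

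**Conclusion.** The point holds as a defect of wording that reaches the primary endpoint. As written, SAP 12.9.1.1 can turn an observed Day 14 success into a failure because of something that happened later, while Flag 01 does not. Neither Protocol 11.1 nor the Per-Protocol repeat settles which applies.

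The size is conditional. It rests on 20% and 5% being failure rates, on 30 per arm, and on an assumed share of Day 14 successes lost by Day 90. Over an assumed 2% to 20% in both arms, exact power runs from 0.81 down to 0.57, against 0.86 with none. Loss in one arm only can hide a true effect or inflate false positives. If the benign reading was programmed, the numerical effect is nil and only the text needs correcting.

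Counting subjects who leave before Day 14 with unknown status as failures follows the protocol and is not challenged.

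**What to change.** In SAP 12.9.1.1 (with X = 14) and 12.9.2.3, replace the sentence with: *Subjects who discontinued before Day X and whose Day X status is not known, or whose status on Day X is otherwise inconclusive, are counted as failures; discontinuation or death after Day X does not change Day X status.*

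In SAP 11.17, state that Flags 01 to 06 follow the same rule. In Protocol 11.1, define non-completer relative to Day 14. That definition should also say how a subject is scored who left before Day 14 but whose Day 14 status is known. The sentence above scores that subject as observed.

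The cost is one sentence in two SAP sections, one line on the flags and a one-line protocol clarification. No new data or subjects are needed. If the tables have already been produced, the report should state which rule was programmed.
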